6. TREATMENT PLAN

After informed consent has been obtained in writing, the subject will then undergo screening procedures and will enter the trial after successful screening. The subject must be willing to undergo a MANDATORY fresh tumor biopsy prior to treatment following successful screening and registration unless the site investigator deems the procedure medically unsafe.

Subjects who have signs and/or symptoms concerning for early clinical progression can undergo imaging before the initial 8 week imaging time point. In this scenario, if there is evidence of radiographic progression as per RECIST version 1.1, subjects will be allocated immediately to Arm B as long as they have received at least 2 doses of nivolumab (two doses of 480mg IV q 4 wks). Subjects who received fewer than 2 doses of nivolumab (480mg dosing) with early progression can either discontinue from study or may continue on to receive at least 2 doses of nivolumab before reassessing response at treating investigator's discretion. The per protocol 8 week scans should still be done on schedule even if earlier scans are done and compared to baseline for initial response assessment which should then be confirmed at the 16 week time point per protocol.

Primary Treatment with Nivolumab

Eligible subjects will be enrolled and will receive primary treatment with nivolumab 480 mg IV (D1) for 2 cycles. Each Cycle = 28 days. After 2 cycles (8 weeks +/- 7 days), all subjects will have initial disease assessment scans.

Arm A: CR or PR Response after Primary Treatment with Nivolumab:

- For subjects allocated to Arm A, nivolumab will be discontinued and subjects will be followed with serial imaging assessments every 8 weeks (Observation).
- If PD develops, therapy with nivolumab 480 mg IV every 4 weeks will be resumed. At this time, subjects will be asked to undergo an optional fresh tumor biopsy. Subjects will have disease assessment scans every 8 weeks (+/- 7 days). Nivolumab will continue until PD is documented.

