7. DOSING DELAYS/DOSE MODIFICATIONS

The NCI Common Terminology Criteria for Adverse Events (CTCAE) v4 will be used to grade adverse events. Subjects enrolled in this study will be evaluated clinically and with standard laboratory tests before and at regular intervals during their participation in this study as specified in Study Calendar & Evaluations. Subjects will be evaluated for adverse events (all grades), serious adverse events, and adverse events requiring study drug interruption or discontinuation.

There will be no dose reductions or dose escalations for either nivolumab or ipilimumab on this study, however, dose delays will be permitted as detailed below for each agent. The descriptions and grading scales found in the revised NCI CTCAE v4 will be utilized for dose delays.

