13: MANDATORY: Blood samples for cfDNA and CTCs will be collected at screening and prior to C1D1 treatment, every 2 cycles (± 7 days) prior to treatment and corresponding to all imaging assessment time points, and at time of EOT visit. Additionally, blood samples for cfDNA and CTCs will be collected at confirmatory imaging assessment time points. If EOT collection is within 2 weeks of prior collection, research samples do not need to be collected. For patients enrolled on the Single Cell Sequencing Cohort, whole blood for CTC collection and whole blood for plasma/PBMC isolation will not be collected.

14: Nivolumab will continue to be administered on D1 of each 28-day cycle. Once confirmatory scans are complete subjects will either be followed per Arm A or Arm B calendar. Subjects that show SD/PD with confirmatory scans after Primary Treatment with nivolumab will be assigned to Arm B. Subjects with SD after initial scans with Primary Treatment with nivolumab and CR/PR with confirmatory scans will have additional scans 8 weeks later (± 7 days) to confirm CR/PR. If CR/PR is confirmed, these subjects will be assigned to Arm A, go into observation and be followed as described in the calendar titled "Arm A: CALENDAR FOR SUBJECTS WITH CR/PR AFTER PRIMARY TREATMENT." Subjects that show CR/PR with confirmatory scans after Primary Treatment with nivolumab will be assigned to Arm A.

ARM A: CALENDAR FOR SUBJECTS WITH CR/PR AFTER PRIMARY TREATMENT	CR/PR after Primary Treatment ⁴ ± 3 days	PD after Observation ⁵ ± 3 days	PD after Re-initiation of nivolumab ⁶ ± 3 days			CR/PR/SD after nivolumab PLUS ipilimumab ⁷ ± 3 days	Every 2 cycles (±7 days) ^{2,3}	End of Treatment Visit ⁸ ± 7 days	Long Term Follow Up ⁹ ± 14 days
Study Evaluation Cycle = 28 days	Observation Cycle 1 +	Re-initiation of Nivolumab	Nivolumab PLUS Ipilimumab			Continued Nivolumab	During Observation and On Treatment	Off Study Treatment; On Study Follow-Up	
	Day 1 ± 3 days	Day 1 ± 3 days	Cycle 1/Day 1 ± 3 days	Cycle 1/Day 22 ± 3 days	Cycle 2/Day 15 +/- 3 days	Day 1 of Cycle 3 onward +/- 3 days	Every 2 cycles (+/- 7 days)	Day 30	Every 6 months
REQUIRED ASSESSMENTS									
Physical Exam	X	X	X	X	X	X		X	
Vital signs and ECOG Performance Status ¹	X	X	X	X	X	X		X	
AEs & concomitant medications	X	X	X	X	X	X		X	X
LABORATORY ASSESSMENTS									
Complete Blood Cell Count with diff (CBC) ²	X	X	X	X	X	X		X	
Comprehensive Metabolic Profile (CMP) ²	X		X	X	X	X		X	
Thyroid Function (TSH and free T4) ²							X	X	

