DISEASE ASSESSMENT									
CT of chest ³							X ³		
CT or MRI of abdomen and pelvis ³							X ³		
TREATMENT EXPOSURE									
Nivolumab		X	X	X		X			
Ipilimumab			X	X					
SPECIMEN COLLECTION									
Tumor Biopsy ¹⁰	X	X						X	
Research Blood Sample- Biomarkers ¹¹	X	X					X	X	
Research Blood Sample- cfDNA and CTCs ¹²	X	X					X	X	
FOLLOW-UP									
Survival Status, Subsequent Therapy									X

Key to Footnotes:

- 1: Vital signs to include upright blood pressure, heart rate, respiratory rate, temperature, oxygen saturation, body weight (kg) and height (cm). Height at SCREENING ONLY.
- 2: Hematology testing to include full CBC with WBC, ANC, hemoglobin, and platelet count and differential. Serum chemistry to include full comprehensive metabolic panel with sodium, potassium, chloride, bicarbonate, BUN, creatinine, glucose, calcium, albumin, AST, ALT, alkaline phosphatase, and total bilirubin. CID1 laboratory assessments do not need to re-meet eligibility criteria. TSH and free T4 will be done every two cycles (8 weeks \pm 7 days), except when ipilimumab is added, TSH and free T4 will be obtained after 3 cycles (12 weeks \pm 7 days) instead of 2 cycles (8 weeks) to align with scans.
- 3: Diagnostic CT chest and CT or MRI of the abdomen and pelvis should be obtained every 2 cycles (\pm 7 days). **NOTE:** When ipilimumab is added, the first set of post-ipilimumab imaging will be obtained after 3 cycles (~12 weeks \pm 7 days) instead of 2 cycles. After the initial set of scans after ipilimumab initiation, the scan timing will revert back to every 2 cycles (\pm 7 days). If dosing is delayed, imaging should follow guidelines of cycles over absolute weeks.
- 4: **OBSERVATION:** Subjects with a CR/PR (Arm A) after Primary Treatment with nivolumab will have nivolumab discontinued and go onto Observation. Radiology imaging will be done every 2 cycles (8 weeks \pm 7 days) as described in bullet 3. Subjects will continue observation until PD. During the observation period subjects will be seen in clinic once per cycles (28 days \pm 3 days). For subjects who have shown persistent CR/PR while on observation, in clinic study visits can be extended to every 8 weeks. A nurse, NP/PA, or physician will call subjects in between visits for assessment of symptoms (at least every 4 weeks). This must be approved by sponsor-investigator prior to modifying subjects visit schedule.

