- 5: **RE-INITIATION OF NIVOLUMAB:** Subjects that experience PD during observation will re-initiate nivolumab. Radiology imaging will be done every 2 cycles (8 weeks \pm 7 days) as described in bullet 3. Subjects will continue nivolumab until PD.
- 6: **ADDITION OF IPILIMUMAB:** Subjects that show PD after re-initiation of nivolumab will have ipilimumab added for 2 doses ONLY. During this time, nivolumab will be given every 3 weeks to match ipilimumab administration. Disease assessment scans will occur after completion of 3 cycles (12 weeks \pm 7 days) from the time ipilimumab is added to nivolumab. Nivolumab ALONE will be continued starting 5 weeks \pm 3 days after last dose of nivolumab PLUS ipilimumab at the start of cycle 3/day 1 from when ipilimumab is added to nivolumab.
- 7: **CONTINUATION OF NIVOLUMAB:** Subjects with CR/PR/SD after initial scans following the addition of ipilimumab to nivolumab will continue nivolumab ALONE until PD. During this time nivolumab will be given every 4 weeks and disease assessment scans will occur every 2 cycles (8 weeks \pm 7 days). Subjects will be permitted to continue treatment beyond site investigator assessed progression as long as they meet the following criteria: (1) Site investigator-assessed clinical benefit AND (2) Subject is tolerating study drug.
- 8: End of treatment (EOT) visit will occur 30 days (\pm 7 days) after last dose of study drug. Subjects will come off study treatment if they have PD as described in bullet #6 or for other reasons such as toxicity or subject choice. Subjects who (1) had study drugs delayed or modified due to toxicity or other factors and (2) were then discontinued from study treatment can use a study visit as EOT visit. Subjects who have an ongoing study treatment-related AE upon discontinuation from the study treatment will be followed until the event has resolved to baseline grade, the event is assessed by the site investigator as stable, new anticancer treatment is initiated, the subject is lost to follow-up, the subject withdraws consent, or until it has been determined that study treatment or participation is not the cause of the AE. If not seen in clinic, subjects will be called on day 100 following the last dose of study drug for assessment of adverse events.

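### The Arm A calendar schedules no metabolic panel during resumed nivolumab, so after the first restart dose no liver or renal chemistry is planned while the drug continues

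*Combined protocol and SAP*

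**What the plan says.** In Arm A, nivolumab stops once a response is confirmed. If the disease then progresses, section 6 says "therapy with nivolumab 480 mg IV every 4 weeks will be resumed" and "Nivolumab will continue until PD is documented". Footnote 5 of the Arm A calendar repeats the rule: "Subjects that experience PD during observation will re-initiate nivolumab".

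Section 7 sets no laboratory timetable of its own. Subjects are to be "evaluated clinically and with standard laboratory tests before and at regular intervals during their participation in this study as specified in Study Calendar", so the calendar is the controlling schedule.

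The row "Comprehensive Metabolic Profile (CMP" in the Arm A calendar is marked for observation, for all three combination columns, for continued nivolumab after the combination, and for the end-of-treatment visit. It is blank for re-initiation of nivolumab, for the every-2-cycles column and for long-term follow-up.

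Footnote 2, which is attached to the laboratory rows, lists the analytes in the panel but gives a frequency only for thyroid tests: "TSH and free T4 will be done every two cycles". Footnote 5 sets imaging times and no laboratory times. Section 6.2 applies the limits in 6.2.1 on day 1 of initial treatment, of the combination, and of resumed nivolumab.

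**The concern.** Read literally, the calendar monitors chemistry more closely off drug than on it. Under footnote 4, "During the observation period subjects will be seen in clinic once per cycles", and the panel is marked at those visits; with a persistent response, "in clinic study visits can be extended to every 8 weeks". When the same subject progresses and goes back on drug, the panel disappears from the schedule.

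Three rules need these values during treatment: the dose-delay rule for AST, ALT and bilirubin (7.1), the liver limits for permanent discontinuation (7.3), and the requirement to report potential drug-induced liver injury as a serious adverse event (12.6). A delay can be triggered at Grade 2, when a subject may have no symptoms, so the examination and adverse event review at these visits do not replace chemistry. Section 2.2 notes that in the phase II nivolumab study in renal cell carcinoma, raised AST was the most common reason for stopping drug because of treatment-related events (two patients).

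A site that followed the calendar exactly would find a silent liver or renal abnormality during resumed nivolumab only through unscheduled testing. The rules could then be triggered late or missed.

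**Working it through.** The plan gives no figure to reproduce. The check is a cell-by-cell reading of the calendars, a search for any other text that fills the gap, and a count of the doses left uncovered.

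**1. Arm A rows side by side**

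| Column | Nivolumab | Blood count | Metabolic panel |
|---|---|---|---|
| Observation, day 1 | – | X | X |
| Re-initiation, day 1 | X | X | **blank** |
| Combination C1D1 | X | X | X |
| Combination C1D22 | X | X | X |
| Combination C2D15 | – | X | X |
| Continued nivolumab, C3 onward | X | X | X |
| Every 2 cycles | – | – | – |
| End of treatment | – | X | X |
| Long-term follow-up | – | – | – |

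The blood count and panel rows differ in one cell, re-initiation day 1. Physical examination, vital signs and adverse event review are also marked in that column, so it is otherwise a full treatment visit.

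**2. All columns in which nivolumab is given**

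- Primary treatment: C1D1 and C2+ day 1 = 2.
- Arm A: re-initiation, C1D1, C1D22 and C3+ = 4.
- Arm B: C1D1, C1D22 and C3+ = 3.
- Total: 2 + 4 + 3 = 9. The blood count is marked in 9 of 9 and the panel in 8 of 9.

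Five of these columns carry 480 mg every 4 weeks: primary C1D1, primary C2+, Arm A re-initiation, Arm A C3+ and Arm B C3+. The panel is marked in 4 of the 5.

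**3. Could another entry supply the panel?**

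- The every-2-cycles column also applies during resumed nivolumab, but it carries thyroid tests, imaging and research bloods only.
- The continued-nivolumab column is for subjects who have already had the combination.
- The observation column ends at progression.
- Footnotes 2 and 5 set no chemistry frequency, and section 7 points back to the calendar.
- Section 6.2.1 has 7 limits, of which 4 need chemistry (creatinine or its clearance, bilirubin, AST, ALT). It applies to the first restart dose only. A recent observation panel might also serve for that dose.

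The next scheduled panel after the restart check is therefore at combination C1D1 or at the end-of-treatment visit.

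**4. Doses left uncovered, per subject**

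Suppose resumed treatment ends with progression at the k-th 8-week scan, with no dose delay and each scan read before the dose due that week.

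- Duration = 8k weeks.
- Doses = 8k / 4 = 2k.
- Doses with neither a scheduled panel nor the 6.2.1 check = 2k − 1.

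| k | Weeks | Doses | Uncovered doses |
|---|---|---|---|
| 1 | 8 | 2 | 1 |
| 2 | 16 | 4 | 3 |
| 3 | 24 | 6 | 5 |

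**5. Subjects affected**

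Only Arm A subjects who restart are affected. The ceiling is the 23 planned for Arm A (section 13.3), and section 13.6 expects that restarts may be few.

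**The case against.** The strongest objection is that the point rests on one missing mark in a table read from a PDF by a program. A mark lost in reading would leave the same picture: an empty cell with its neighbours in place. The calendars show other small irregularities, such as a garbled C1D1 in the Arm A laboratory footnote and a plus-or-minus sign reduced to a minus in an Arm B footnote. A panel present in 8 of 9 dosing columns, and even off drug, also looks more like a slip than a decision. This stands as a limit on confidence. It does not remove the point, because no text elsewhere supplies the missing schedule, and the sponsor can settle the matter by looking at the original table.

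A second objection is that sections 7.1 and 7.3 apply to nivolumab with or without ipilimumab and do not exempt resumed treatment, so a careful site would draw chemistry in order to apply them. Many sites probably would. But those rules say what to do with a value, not when to obtain it, and section 7 leaves timing to the calendar.

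A third objection is that few subjects are involved and that the dose count measures exposure, not harm. That is correct, and it limits the weight of the point.

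**Conclusion.** The concern holds. As the calendar reads, chemistry is scheduled at observation visits off drug and in every other nivolumab column, but not during resumed nivolumab. The first restart dose is covered in substance by section 6.2.1; later doses are not. The gap is 1, 3 or 5 doses per subject for resumed treatment lasting 8, 16 or 24 weeks, under the timing assumptions above, in at most 23 subjects and perhaps far fewer. It is a safety-monitoring gap that should be corrected, and it has no effect on endpoints, power or error rates. Confidence is medium, because a mark lost in reading the PDF cannot be ruled out. The number of abnormalities that would go undetected cannot be estimated from the documents.

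**What to change.** First check the original Arm A calendar. If the cell is blank there, mark the metabolic panel on day 1 of the re-initiation column, so that it is drawn with the blood count at every resumed-nivolumab visit, as in the other four columns for 480 mg every 4 weeks.

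An optional clarification is to state in the calendar laboratory footnotes that the section 6.2.1 limits still apply on day 1 of initial, combination and resumed treatment. Those footnotes now say that C1D1 laboratory values need not meet eligibility again, which could be misread as waiving those limits.

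The cost is one calendar mark, one routine panel per resumed visit on blood already being drawn, and an occasional delayed dose.

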6.7 Treatment Beyond Disease Progression

Accumulating evidence indicates a minority of subjects treated with immunotherapy may derive clinical benefit despite initial evidence of PD. Subjects will be permitted to continue treatment beyond site investigator assessed progression after the administration of ipilimumab for rescue as detailed in the study schema and continued nivolumab as long as they meet the following criteria:

- Site investigator-assessed clinical benefit
AND
- Subject is tolerating study drug(s).

The assessment of clinical benefit should take into account whether the subject is clinically deteriorating and unlikely to receive further benefit from continued treatment. All decisions to continue treatment beyond progression on nivolumab after addition of ipilimumab should be discussed with the sponsor-investigator and documented in the study records.

Subjects should discontinue study therapy upon evidence of further progression on nivolumab after administration of ipilimumab, defined as an additional 10% or greater increase in tumor burden volume from time of initial progression (including all target lesions and new measurable lesions).

New lesions are considered measurable at the time of progression if the longest diameter is at least 10 mm (except for pathological lymph nodes, which must have a short axis of at least 15 mm). Any new lesion considered non-measurable at the time of initial progression may become measurable and therefore included in the tumor burden measurement if the longest diameter increases to at least 10 mm (except for pathological lymph nodes, which must have an increase in short axis to at least 15 mm) on followup imaging.

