10.3 Response Criteria

10.3.1 Evaluation of Target Lesions

Complete Response (CR): Disappearance of all target lesions. Any pathological lymph nodes (whether target or non-target) must have reduction in short axis to <10 mm.

Partial Response (PR): At least a 30% decrease in the sum of the diameters of target lesions, taking as reference the baseline sum diameters.

Progressive Disease (PD): At least a 20% increase in the sum of the diameters of target lesions, taking as reference the smallest sum on study (this includes the baseline sum if that is the smallest on study). In addition to the relative increase of 20%, the sum must also demonstrate an absolute increase of at least 5 mm. (Note: the appearance of one or more new lesions is also considered progression). For subjects who demonstrate PD at the first on-treatment imaging assessment, subjects will be allowed to remain on study until confirmatory imaging at the next imaging assessment at the discretion of the treating investigator if it appears that the subjects is clinically benefiting from treatment.

Stable Disease (SD): Neither sufficient shrinkage to qualify for PR nor sufficient increase to qualify for PD, taking as reference the smallest sum diameters while on study.

If a target lesion is biopsied at screening, this lesion must be followed as non-target lesion after the biopsy unless it is the patient's only target lesion. If there is only one target lesion, it should be followed as a target lesion regardless.

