10.3.4 Evaluation of Best Overall Response

The best overall response is the best response recorded from the start of the treatment until disease progression/recurrence (taking as reference for progressive disease the smallest measurements recorded since the treatment started). The subject's best response assignment will depend on the achievement of both measurement and confirmation criteria.

Table 2: For Subjects with Measurable Disease (i.e., Target Disease)

Target Lesions	Non-Target Lesions	New Lesions	Overall Response	Best Overall Response when Confirmation is Required*
CR	CR	No	CR	>4 wks Confirmation**
CR	Non-CR/Non-PD	No	PR	≥4 wks Confirmation**
CR	Not evaluated	No	PR	
PR	Non-CR/Non-PD/not evaluated	No	PR	
SD	Non-CR/Non-PD/not evaluated	No	SD	Documented at least once ≥4 wks from baseline**
PD	Any	Yes or No	PD	

Any	PD***	Yes or No	PD	no prior SD, PR or CR
Any	Any	Yes	PD	

* See RECIST 1.1 manuscript for further details on what is evidence of a new lesion.
 ** Only for non-randomized trials with response as primary endpoint.
 *** In exceptional circumstances, unequivocal progression in non-target lesions may be accepted as disease progression.
NOTE: Subjects with a global deterioration of health status requiring discontinuation of treatment without objective evidence of disease progression at that time should be reported as “*symptomatic deterioration.*” Every effort should be made to document the objective progression even after discontinuation of treatment.

Table 3. For Subjects with Non-Measurable Disease (i.e., Non-Target Disease)

Non-Target Lesions	New Lesions	Overall Response
CR	No	CR
Non-CR/non-PD	No	Non-CR/non-PD*
Not all evaluated	No	not evaluated
Unequivocal PD	Yes or No	PD
Any	Yes	PD
* ‘Non-CR/non-PD’ is preferred over ‘SD’ for non-target disease since SD is increasingly used as an endpoint for assessment of efficacy in some trials so to assign this category when no lesions can be measured is not advised		

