13.6 Operating Characteristics of Early Futility Stopping

True-unknown PD rate (%)	Probability of observing 5 or more PD among 9 subjects
30	0.03
40	0.1
50	0.25
60	0.48
70	0.73

For subjects who re-start nivolumab due disease progression, given there is no prior data for this treatment strategy, and the expected number of subjects to re-start nivolumab maybe small, the study team will monitor the non-response rate carefully. Similar futility analysis may take place at the subsequent image assessment to assess the risk of subjects no longer respond to nivolumab and decide if the strategy is not safe for subjects. The exact criteria will be determined as deemed clinically relevant.

Arm B: The safety review will be concurrent with the first efficacy review of PR/CR that is specified by the Simon two-stage design. Review of these safety data will be conducted by the study team and an independent DFCI Data and Safety Monitoring Committee (DSMC). Based on the review, the DSMC may advise that the study regimen be suspended for additional review. After this initial safety assessment, toxicity and adverse event data will be evaluated as part of the recurrent trial review by the DSMC.

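### Arm A names no reference scan for progression after the nivolumab restart, so the nadir-based definition can call an unchanged tumour progressive

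*Combined protocol and SAP*

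**What the plan says.** Section 2.7, the Arm A part of Section 6 and footnotes 5 and 6 of the Arm A calendar describe one sequence. A confirmed responder stops nivolumab. Progression during observation brings nivolumab back, with scans every 8 weeks. It runs until progression, and progression at that stage adds ipilimumab: "Subjects that show PD after re-initiation of nivolumab will have ipilimumab added for 2 doses ONLY".

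Section 10.3.1 defines RECIST progression as "At least a 20% increase in the sum of the diameters of target lesions, taking as reference the smallest sum on study". It adds that "the sum must also demonstrate an absolute increase of at least 5 mm" and that "the appearance of one or more new lesions is also considered progression". Stable disease in the same section is judged "taking as reference the smallest sum diameters while on study". Section 10.3.4 repeats the nadir reference for best overall response ("taking as reference for progressive disease the smallest measurements recorded since the treatment started"), and 10.4 repeats it for duration of response. Partial response, by contrast, is measured from the baseline sum. Section 13.7.1 applies RECIST 1.1 at every restaging.

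One rule does measure from a progression scan. Section 6.7 ends treatment on further growth of 10% or more since initial progression, but its scope is stated: "Subjects should discontinue study therapy upon evidence of further progression on nivolumab after administration of ipilimumab".

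On what happens after a restart, 13.6 says that "the study team will monitor the non-response rate carefully". It adds that a futility analysis may be done at a later scan, with criteria to be settled then.

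**The concern.** Every Arm A subject who restarts nivolumab has PD on the day of restart. The useful question at the next scan is whether resumed nivolumab is controlling the disease. The nadir reference answers a different one: whether the tumour is still well above its smallest recorded size. A tumour that regrew off drug and then stopped growing on drug can meet the written trigger for ipilimumab without any growth on nivolumab.

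Two things depend on this. The first is who moves to ipilimumab; once it is given, the effect of restarting nivolumab alone can no longer be observed in that subject. The second is the evidence under 13.6 on whether a response lost off drug can be regained, which is the safety question behind the Arm A strategy.

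**Working it through.** The plan states no figure on this point, so there is none to reproduce. The check applies the 10.3.1 rule to the scan after restart.

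**Inputs from 10.3.1.** PD needs a sum at least 20% above the reference and at least 5 mm above it. PR needs a fall of at least 30% from baseline.

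**Assumed inputs.** The tumour sums are mine; the documents give none. Let N be the nadir sum, r × N the sum at restart, and S the sum at the next scan.

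**Rule with the nadir as reference.** PD persists while S ≥ max(1.2 × N, N + 5). The 5 mm term decides when 0.2 × N < 5, that is, when N is below 25 mm. For N of 25 mm or more, the fall from restart must exceed 1 − 1.2/r before PD lifts.

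| Restart sum ÷ nadir (r) | Fall from restart that must be exceeded |
|---|---|
| 1.20 | 0% |
| 1.24 | 3.2% |
| 1.30 | 7.7% |
| 1.40 | 14.3% |
| 1.60 | 25.0% |
| 1.75 | 31.4% |
| 2.00 | 40.0% |

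A 30% fall is not enough once r exceeds 1.2 ÷ 0.7 = 1.71.

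**Both references side by side.** I took nadirs of 30, 50 and 70 mm, r from 1.2 to 2.0, and changes since restart from +10% to −29%. Against the nadir, every case with 0% or +10% change is PD. Against the restart scan, no case is PD.

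**Three worked cases.**

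- *Unchanged tumour.* Nadir 50, restart 62 (+24%, +12 mm), next scan 62 mm. Against the nadir this is PD; against the restart scan the change is 0%.
- *Real shrinkage still called PD.* Nadir 30, restart 60, next scan 42 mm. The fall from restart is 18/60 = 30%. Against the nadir the sum is 42/30 = 1.40 times and 12 mm above, so it is PD.
- *Small shrinkage called PR.* Baseline 100, nadir 50, restart 62, next scan 58 mm. Against the nadir, 58/50 = 1.16, so it is not PD. Against baseline it is 42% lower, so it is PR. The fall from restart is 4/62 = 6.5%.

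The last two cases show that the standard references can misstate response to resumed nivolumab in either direction.

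**Small nadirs.** With nadir 10 mm and restart 15 mm (+50%), the limit is max(12, 15) = 15 mm, so any shrinkage lifts PD. The table does not apply there, and low nadirs are plausible in an arm selected for response.

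**New lesions.** If PD at restart came from a new lesion that persists, the overall-response table in 10.3.4 still gives PD wherever a new lesion is recorded. This is less certain than the target-lesion case, because 10.3.1 speaks of a lesion appearing, and one already recorded at restart does not clearly appear again.

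**The case against.** The strongest reply is that nobody would read the trigger this way. Sections 2.7 and 6 call the second progression a subsequent one. Since the subject already has PD at restart, continuing nivolumab until PD most naturally means a new progression. Section 6, under the text for either arm, also allows treatment beyond progression when the investigator sees benefit and the drug is tolerated. The move to ipilimumab is therefore not strictly automatic.

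This stands in part. It shows that the nadir reading is the literal default and not the only reading. It does not supply a reference scan, footnote 6 omits the qualifier, and the allowance is discretionary and leaves the PD label as it was. Section 10.3.2 sends the reader to 6.7 for progression on continued treatment, and 6.7 covers only the period after ipilimumab. Sites could reasonably apply different rules.

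A reader might also infer four stronger things that the documents do not support:

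- *The triggering PD always carries forward to the next scan.* It does not: modest shrinkage lifts target-lesion PD when the restart sum is close to 1.2 times nadir.
- *The main results are biased.* They are not. PD in observation has already ended the one-year response and is already the PFS event, and the salvage-free interval ends at the restart itself.
- *Stable subjects called PD inflate the non-response rate in 13.6.* Where the plan does split response from non-response (13.7.3, Arm B), response means PR or CR. On that usage SD and PD are both non-response, so relabelling one as the other moves nobody.
- *Section 13.6 commits to a safety decision on this rate.* It says only that an analysis may take place, with criteria still open.

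**Conclusion.** The point holds in a limited form. As written, the trigger for ipilimumab in Arm A rests on a PD definition that an unchanged tumour still satisfies after the restart, and the one rule that resets the reference does not reach this phase. This is a stated rule that misfires if applied literally, and other wording in the protocol points away from it.

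The consequences are confined to two places: which restarted subjects receive ipilimumab, and any assessment of response after restart under 13.6. That assessment can err both ways, through PD against nadir and PR against the original baseline.

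The shrinkage thresholds follow exactly from 10.3.1 for nadirs of 25 mm or more; the example sums are assumed. I give no count of affected subjects. The documents state neither how many subjects will restart nor how much tumours change afterwards, and the stable-disease rates they quote are for initial nivolumab treatment, not re-treatment of earlier responders.

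**What to change.** Reconcile 2.7, Section 6 (Arm A and the text for either arm), 6.7, footnotes 5 and 6 of the Arm A calendar, and 10.3.1 so that one reference scan is named for progression after the restart. The clinical trigger itself is for the sponsor to set.

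For any post-restart analysis under 13.6, state in advance that response and non-response are measured against the scan that triggered the restart, with lesions present on that scan counted as existing. Report the nadir-based RECIST call alongside, so that the effect of the reference is visible.

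The cost is a few sentences of protocol text and one added reference in the tumour-assessment derivation. No extra scans are needed.
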